6.0 CLINICAL ASSESSMENTS/PROCEDURES

6.1 Schedule of Assessments

The procedures and measurements to be evaluated at each study visit are shown in Table 1, Schedule of Assessments.

Table 1: Schedule of Assessments:

Evaluation ¹	Visit 1 Day -10 to Day -7	Dosing Phase (14 Days)		Follow-Up Phase (15 Days)	
		Visit 2 Day 1	Visit 3 Day 7 (+/- 1)	Visit 4 Day 15 (+ 1)	Visit 5 Day 29 (+/- 2)
Written Informed Consent	X				
Demographics	X				
Entry Criteria	X	X			
Medical/Medication History	X	X			
Urine Pregnancy Test		X			X
Slit Lamp Biomicroscopy ²	X	X	X	X	X
Clinical Signs Evaluation	X	X	X	X	X
Subject-Reported Eyelid Irritation	X	X	X	X	X
Intraocular Pressure	X	X	X	X	X
Best Corrected Visual Acuity	X	X	X	X	X
Ophthalmoscopy ²	X			X	X ³
Confirm non-prescription Lid Scrub Use ⁴	X	X	X	X	X
Confirm and Document Subject Eligibility	X	X			
AE Assessment	X	X	X	X	X
Randomization		X			
Dispense IP and Dosing Diary		X			
Instruct Subject on IP and Dosing Diary		X			
Update Concomitant Medications		X	X	X	X
Review IP and Dosing Diary		X	X	X	X ³
Collect IP and Dosing Diary				X	X ³
Exit Subject From Study					X

AE = Adverse Event; BSIQ= Blepharitis Symptoms and Impacts Questionnaire; eCRF = electronic case report form; IP = Investigational Product.

¹Some procedures are completed for both eyes, study eye only, or eye(s) dosed with IP, depending on the visit.

²Performed by a board-certified ophthalmologist

³If not completed at previous visit

⁴Use of non-prescription lid scrubs is required for at least 7 days prior to Visit 2 and throughout the study period (prescription lid scrubs are prohibited)

Note: Unscheduled visits may occur during the study period. All assessments will be recorded on the eCRF for unscheduled visits, but it is up to the investigator which assessments to conduct. If the subject exits early, all Visit 5 assessments should be conducted, including ophthalmoscopy if not obtained at Day 15 (Visit 5).

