6.2 Examination Procedures

The following ophthalmic examinations will be conducted at intervals specified in Table 1 Schedule of Assessments.

- **Clinical Signs and Symptom:** The clinical signs of blepharitis: eyelid redness, eyelid swelling and eyelid debris will be evaluated at every visit and will be scored by the investigator using a 0-3 grading scale. The subject symptom of eyelid irritation will also be evaluated at every visit and graded by the subject using a 0-3 grading scale.
- **Best Corrected Visual Acuity (BCVA):** BCVA will be measured at every visit. The Early Treatment Diabetic Retinopathy Study (ETDRS) log of the minimum angle of resolution (logMAR) will be used to measure BCVA. As appropriate, Lea Symbols® will be used in children.
- **Intraocular Pressure (IOP):** IOP will be measured in mmHg using an applanation tonometer at every visit. IOP is to be measured in all subjects.
- **Ophthalmoscopy:** Ophthalmoscopy will be performed by a board-certified ophthalmologist at Day -10 to -7 (Visit 1) and Day 15 (Visit 4) or Day 29 (Visit 5) if not completed at Visit 4.
- **Biomicroscopy:** Slit lamp biomicroscopy will be performed at every visit during the study to observe the overall health of the eye, including the lid/lashes, conjunctiva, cornea anterior chamber, iris, and lens. Any observations at the screening visit should be recorded as ocular medical history, and any new or worsened observations may be recorded as AEs. Slit lamp biomicroscopy will be conducted by a board-certified ophthalmologist at every visit.

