7.4 Follow-up of Adverse Events and Serious Adverse Events

All AEs, regardless of severity, will be followed throughout the study to the final study visit, until they resolve or resolve with sequelae (as judged by the investigator).

At the final study visit, new AEs, as well as follow-up information for continuing AEs, will be recorded in the eCRF and source document. Non-serious ongoing AEs will be followed beyond the final study visit at the discretion of the investigator and recorded in the source documents.

If an SAE is unresolved at the final study visit, it will be followed by the investigator until it resolves or resolves with sequelae (as judged by the investigator). Follow-up data for such SAEs will be recorded in the source document and reported to the sponsor or designee.

Subjects withdrawn from the study due to an AE or SAE will be followed by the investigator until the outcome is determined (resolved or resolved with sequelae) and, where appropriate, additional written reports and documentation will be provided to the sponsor.

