4.0 STUDY ENDPOINTS

4.1 Primary efficacy endpoint

The primary efficacy endpoint is the reduction in the Day 1 (baseline) total clinical sign and symptom score (eyelid swelling, eyelid redness, eyelid debris, and eyelid irritation) by at least 2 units at Day 15 with no worsening of any sign or symptom.

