4.2 Secondary efficacy endpoint

The secondary efficacy endpoint is complete resolution of eyelid irritation at Day 15.

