5.1 Intention-to-Treat (ITT) Analysis Set

The ITT analysis dataset includes all randomized subjects regardless of whether post-baseline measures are collected or IP is received. Subjects in the ITT dataset will be analyzed in the treatment group to which they were assigned by the randomization scheme, regardless of which IP, if any, they receive.

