6.2 Handling of missing data and/or invalid data and outliers

6.2.1 Missing data analysis methods for efficacy data

The sensitivity analyses of the primary and/or secondary efficacy endpoints will be performed using Last Observation Carried Forward (LOCF) will be assessed.

In LOCF, missing Day X values will be imputed using the last non-missing observation prior to Day X.

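### The plan does not separate stopping study product from leaving the study and requires no Day 15 score after early stopping, so subjects who leave before Day 15 have a carried-forward outcome

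*Protocol*

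**What the plan says.** **Endpoints.** Both are fixed at Day 15. The primary is a fall in the total score "by at least 2 units at Day 15 with no worsening of any sign or symptom" (SAP 4.1). For the other, SAP 4.2 states: "The secondary efficacy endpoint is complete resolution of eyelid irritation at Day 15".

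**Analysis set.** The ITT set "includes all randomized subjects regardless of whether post-baseline measures are collected or IP is received" (SAP 5.1).

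**Early exit.** The note under Table 1 reads: "If the subject exits early, all Visit 5 assessments should be conducted, including ophthalmoscopy if not obtained at Day 15 (Visit 5". In Table 1 itself, and in Protocol 6.2, Day 15 is Visit 4 and Day 29 is Visit 5.

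**Withdrawal for an adverse event.** Protocol 7.4: "Subjects withdrawn from the study due to an AE or SAE will be followed by the investigator until the outcome is determined". It mentions no efficacy scoring during that follow-up.

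**Scoring.** The three signs are graded by the investigator at every visit, and for the symptom Protocol 6.2 says: "The subject symptom of eyelid irritation will also be evaluated at every visit and graded by the subject using a 0-3 grading scale". The Visit 5 set used at exit therefore contains all four components of the total score.

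**Missing scores.** SAP 7.1 makes last observation carried forward (LOCF) the general rule for the primary and secondary tests. SAP 7.4.3 repeats it for the secondary endpoint. SAP 7.4.2 names no imputation for the primary. SAP 6.2.1 presents LOCF as a sensitivity analysis and defines it: "missing Day X values will be imputed using the last non-missing observation prior to Day X".

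**The concern.** The ITT question is response at Day 15 in everyone randomised, whether or not they took the product. Answering it needs a Day 15 score from subjects who stopped early. The plan never says that such subjects stay in the study for Visit 4, and its wording on adverse events moves straight to withdrawal from the study. Some of those withdrawn will still be in contact with the site around Day 15 because of the event, yet no eyelid or irritation score is asked for.

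The missing value is then replaced by an earlier one. An ISV-305 subject who had improved by the exit assessment and left because of an adverse event can count as a Day 15 responder, whatever happened after the drug was stopped. Reasons for leaving plausibly differ between a steroid and its vehicle, so the errors need not cancel. At stake is some bias of unknown direction and size in both efficacy comparisons, from data that a visit already on the schedule could supply.

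**Working it through.** **1. Trace a subject who leaves before Day 15.**

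| Situation | What the plan yields at Day 15 |
|---|---|
| Stops product, stays in the study | Observed score at Visit 4 under Table 1, but no text says the subject is kept |
| Leaves on Day 10 with an exit assessment | Exit score carried forward, since Day 10 precedes Day 15 |
| Leaves with no exit assessment, seen at Day 7 | Day 7 score carried forward |
| Leaves with no post-baseline score | Baseline carried forward, which the LOCF definition does not exclude: a non-responder on both endpoints |
| Leaves after a scored Day 15 visit | Unaffected |

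The second row relies on SAP 6.1, which counts study days from the first dose by assessment date, and on the LOCF definition, which refers to a day and not to a visit number. In the fourth row the change is 0, below the required 2 units. Irritation is at least 1 at entry (Protocol 3.2), so it is not resolved.

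**2. The plan's own figures.** The allocation reproduces: 550 × 2/3 = 366.7 and 550/3 = 183.3, against 366 and 184. The total of 550 cannot be reproduced, because the text available gives no power, response rates or dropout rate.

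**3. Subjects affected (assumed share e leaving before Day 15).**

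| e | Of 550 | ISV-305 (366) | Vehicle (184) |
|---|---|---|---|
| 2% | 11 | 7.3 | 3.7 |
| 5% | 27.5 | 18.3 | 9.2 |
| 10% | 55 | 36.6 | 18.4 |

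**4. Shift in the treatment difference.** Let L be the responder share under LOCF among leavers and T their true Day 15 share, with subscripts A for ISV-305 and V for vehicle:

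shift = e_A × (L_A − T_A) − e_V × (L_V − T_V)

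With the error confined to one arm:

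- 5% leaving, 20-point gap: 0.05 × 0.20 = 1.0 point
- 5% leaving, 30-point gap: 0.05 × 0.30 = 1.5 points
- 10% leaving, 20-point gap: 0.10 × 0.20 = 2.0 points
- 10% leaving, 30-point gap: 0.10 × 0.30 = 3.0 points

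At 2% leaving with a 20-point gap it is 0.4 point. With the same error in both arms it vanishes: 0.10 × 0.20 − 0.10 × 0.20 = 0. The mathematical limit, with every leaver misclassified and in opposite directions by arm, is 2e: 4, 10 or 20 points for 2%, 5% or 10%. That is a bound, not an expectation.

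**5. Yardstick.** The smallest observed difference that reaches two-sided p < 0.05 by Fisher's exact test, for assumed vehicle response rates:

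| Vehicle rate | Responders, ISV-305 / vehicle | Difference |
|---|---|---|
| 20% | 102/366 vs 37/184 | 7.8 points |
| 30% | 141/366 vs 55/184 | 8.6 points |
| 40% | 181/366 vs 74/184 | 9.2 points |
| 50% | 216/366 vs 92/184 | 9.0 points |

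A shift of 1 to 3 points is between 1/9.2 = 11% and 3/7.8 = 38% of that threshold.

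**The case against.** The strongest reply is that much of this is inference from silence. Each part deserves a separate answer.

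- **A reader might infer that anyone who stops product is lost to efficacy scoring.** The documents do not say so. The Table 1 note concerns leaving the study, and a subject who stops product but stays would have Visit 4. What stands is that the plan neither draws the distinction nor requires retention.
- **A reader might infer that exit data are filed as Visit 5**, so that an older Day 7 score is carried forward and an on-treatment intraocular pressure enters the Day 29 summary. No text files exit data that way, and the study-day and LOCF definitions point against it. What stands is that no explicit assignment rule is given.
- **A reader might take LOCF as settled for the primary endpoint.** It rests on SAP 7.1 alone, and SAP 6.2.1 conflicts with it. Only the secondary endpoint is explicit.
- **Subjects withdrawn for an adverse event may not be in contact at Day 15.** The event may have resolved by then. Unscheduled visits are also allowed, with assessments at the investigator's choice. So the score is not required, which is different from being forbidden.
- **Withdrawal text may exist outside the public version.** Protocol 3.0 mentions withdrawal in its title but shows no such text. If a rule exists, the sponsor need only confirm it and align the note.
- **The Visit 5 label for Day 15 looks like a slip.** Agreed: Protocol 6.2 has the mapping that matches Table 1. It still needs reconciling.

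**Conclusion.** The point holds in a limited form. The text available does not separate stopping product from leaving the study, and does not require a Day 15 score after early stopping. It fills the gap for leavers with a carried-forward value, although its ITT set is defined without regard to product received. For the primary endpoint, the role of LOCF also has to be reconciled between SAP 6.2.1 and 7.1.

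The exit assessment softens the problem, because it scores all four components and, by study day, is the value carried.

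The size of any bias cannot be judged from the documents. The 1 to 3 points rest on assumed exit rates of 5% to 10% and an assumed error of 20 to 30 points in one arm only. Rarer exits, or similar errors in both arms, make the shift smaller or zero. This is a worthwhile and cheap improvement in data collection; it does not show that the primary result would be wrong.

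**What to change.** **Protocol, Table 1 note.** Keep the present instruction for subjects who do leave, including any outstanding ophthalmoscopy, and add:

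> A subject who stops IP early, for whatever reason, stays in the study and attends Visit 4 (Day 15) and Visit 5 (Day 29) on schedule, with signs and irritation scored, unless consent to further visits is withdrawn.

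Reconcile the visit label given to Day 15 in the note with Table 1 and Protocol 6.2.

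**SAP.** State that the observed Day 15 score is used in the ITT analysis whether or not product was continued. State that an exit assessment is assigned by study day. Name the handling of missing Day 15 scores for the primary endpoint in 7.4.2, and bring 6.2.1 and 7.1 into agreement.

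**Cost.** A few sentences in the protocol and SAP; Visits 4 and 5 are already on the schedule. Some subjects will have follow-up they would otherwise have avoided, and scores taken off drug may slightly dilute the observed effect. The change concerns data collection only and takes no position on when treatment should stop.

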6.2 Examination Procedures

The following ophthalmic examinations will be conducted at intervals specified in Table 1 Schedule of Assessments.

- **Clinical Signs and Symptom:** The clinical signs of blepharitis: eyelid redness, eyelid swelling and eyelid debris will be evaluated at every visit and will be scored by the investigator using a 0-3 grading scale. The subject symptom of eyelid irritation will also be evaluated at every visit and graded by the subject using a 0-3 grading scale.
- **Best Corrected Visual Acuity (BCVA):** BCVA will be measured at every visit. The Early Treatment Diabetic Retinopathy Study (ETDRS) log of the minimum angle of resolution (logMAR) will be used to measure BCVA. As appropriate, Lea Symbols® will be used in children.
- **Intraocular Pressure (IOP):** IOP will be measured in mmHg using an applanation tonometer at every visit. IOP is to be measured in all subjects.
- **Ophthalmoscopy:** Ophthalmoscopy will be performed by a board-certified ophthalmologist at Day -10 to -7 (Visit 1) and Day 15 (Visit 4) or Day 29 (Visit 5) if not completed at Visit 4.
- **Biomicroscopy:** Slit lamp biomicroscopy will be performed at every visit during the study to observe the overall health of the eye, including the lid/lashes, conjunctiva, cornea anterior chamber, iris, and lens. Any observations at the screening visit should be recorded as ocular medical history, and any new or worsened observations may be recorded as AEs. Slit lamp biomicroscopy will be conducted by a board-certified ophthalmologist at every visit.

7.0 EVALUATION, RECORDING AND REPORTING OF ADVERSE EVENTS

All AEs either observed by the investigator or study site staff or reported by the subject spontaneously or in response to a direct question regarding the subject's health by the investigator will be recorded in the source document and AE eCRF.

Events reported before signing the consent form should be recorded as medical history; once the ICF is signed new conditions or worsening of existing conditions or episodes that increase in frequency should be recorded as AEs in the source document and AE eCRF.

To standardize the collection of AEs during a study, subjects should be asked a standard question to elicit AEs: "Have you had any problems since your last visit or telephone call?" and "What is the status of [list previously reported unresolved AEs]?" Subjects will also be instructed to contact the investigator immediately if they note any unusual systemic or ocular AEs between visits.

Throughout the course of the study, the investigator must remain alert to possible adverse experiences or untoward findings. If adverse experiences occur, the first concern will be the safety of the subject. Appropriate medical intervention will be provided by the investigator.

The collection, review and management of safety data (AEs and SAEs) will be conducted in compliance with the requirements of the FDA as well as the local IRB/Independent Ethics Committee (IEC).

7.1 Definitions

Adverse Event

An AE is any untoward medical occurrence associated with the use of an IP in humans, whether or not considered related to the IP.

An AE can therefore be any unfavorable and unintended sign (including an abnormal laboratory finding, for example), symptom, or disease temporally associated with the use of an IP, without any judgment about causality. An AE can arise from any use of the IP (e.g., off-label use, use in combination with another drug) and from any route of administration, formulation or dose, including overdose.

Medical conditions or diseases present before a subject starts study treatment are only considered AEs if they worsen after the subject signs informed consent.

Diagnostic and therapeutic non-invasive and invasive procedures, such as surgery, should not be reported as AEs. However, the medical condition for which the procedure was performed should be reported if it meets the definition of an AE. For example, an acute appendicitis that begins during the AE-reporting period should be reported as the AE and the resulting appendectomy noted according to the eCRF completion guideline.

Adverse Event Reporting Period

The AE reporting period for this study begins upon signing the consent form and ends at the completion of the subjects' final visit exam. All AEs that occur in study subjects during the AE-reporting period must be reported in the source documents and on the AE eCRF, whether or not the event is considered related to the IP. In addition, any known untoward event that occurs subsequent to the AE reporting period that the investigator assesses as possibly related to the IP should be recorded in the source documents and reported to the sponsor or designee.

Serious Adverse Event (SAE)

An SAE is an event that, in the view of either the investigator or sponsor, results in any of the following outcomes:

- death
- a life-threatening AE or sight-threatening AE, where ophthalmics are involved
- inpatient hospitalization or prolongation of existing hospitalization
- a persistent or significant incapacity or substantial disruption of the ability to conduct normal life functions
- a congenital anomaly/birth defect

- an important medical event that may not result in death, be life-threatening/sight-threatening, or require hospitalization may be considered serious when, based upon appropriate medical judgment, they may jeopardize the subject and may require medical or surgical intervention to prevent one of the outcomes listed above. Examples of such events are intensive treatment in emergency room or at home for allergic bronchospasm; blood dyscrasias or convulsions that do not result in hospitalization; or development of drug dependency or drug abuse.

The criterion of inpatient hospitalization is met if the subject is admitted to the hospital as the result of an AE, even if the subject is released on the same day. An emergency room visit does not qualify as “inpatient hospitalization” unless the subject is admitted to the hospital during the visit; however, the reason for the emergency room visit may qualify as an SAE based on another SAE criteria (e.g., life threatening or medically significant event).

Pre-existing Conditions

In this study, a pre-existing condition is a disorder/disease present before the AE-reporting period starts (i.e., prior to the subject signing the ICF) and noted on the Medical History eCRF. A pre-existing condition should not be reported as an AE unless the condition worsens or episodes increase in frequency during the AE-reporting period.

7.2 Adverse Events Associated with Study Procedures

Visual Acuity

A worsening of BCVA of 3 lines or more in logMAR score should be captured in the source documents and the appropriate AE eCRF.

IOP

An increase in IOP of ≥ 10 mmHg from Visit 1 or any subsequent visit should be captured as an AE in the source documents and on the AE eCRF.

Biomicroscopy

Slit lamp biomicroscopy will be performed during the study to observe the overall health of the eye, including the lid/lashes, conjunctiva, cornea, anterior chamber, iris, and lens. Any observations prior to signing the ICF should be recorded as ocular medical history. Any new or worsened observations after signing the ICF may be recorded as an AE.

Ophthalmoscopy

A new finding or a significant worsening (2 units or more) from Visit 1 should be recorded as an AE.

7.3 Reporting and Evaluation of AEs and SAEs

Table 2Table 2 presents the reporting guidelines for AEs and SAEs. It is important that the investigator comply with the SAE reporting timelines in order to assure that safety reporting timelines of IRB/IEC and regulatory authorities such as the FDA can be met.

Table 2: Requirements for Reporting Adverse Events and Serious Adverse Events to Sponsor

Type	Reporting Time	Type of Report
Serious	Within 24 hours	Adverse Event Report (AE eCRF) Serious Adverse Event Report Form
Non-serious	Per eCRF submission procedure	Adverse Event Report (AE eCRF)

All information relevant to the SAE must be recorded on the appropriate SAE Report Form, and the form submitted immediately (within 24 hours of learning of the event) to the sponsor Medical Monitor or designee.

The investigator must also provide sponsor or designee a copy of all pertinent medical records such as source documents, hospitalization records, death certificates etc. that are de-identified and contain only the study subject number and the subject initials. The investigator should maintain a copy of these medical records in his/her files, as well as any information and medical judgments from colleagues or other medical personnel who assisted in the treatment and follow-up of the subject.

The investigator should ensure that the subject receives appropriate medical treatment and follow-up. Subjects should receive follow-up until the SAE resolves or resolves with sequelae (as judged by the investigator).

Institutional Review Board or Independent Ethics Committee

The investigator will inform the IRB/IEC of any SAE/serious, unexpected, suspected adverse reaction according to the IRB/IEC's specific reporting guidelines.

For all serious, unexpected, suspected adverse reactions, the sponsor or designee will provide documentation to the investigator for the investigator's report to the IRB/IEC or local regulatory authorities.

The investigator must provide documentation of all such IRB/IEC notifications to the sponsor or designee. Copies of each report must be kept in the investigator's files.

